#### 8.2.3. Global Aesthetic Improvement Scales (GAIS)

The Investigator's and the subject's assessments of global facial aesthetic improvement as measured by the 5-point GAIS at post-treatment visits beginning at Day 30 after last treatment received (see Protocol Appendix 6) will be summarized using summary statistics for categorical data for the ES. GAIS responses will be listed for the FAS.

#### 8.2.4. Natural Look and Feel/Product Smoothness/Dynamic Lip Lines

Subject's assessment of natural look and feel of their lips as measured by the 5-point Likert scale at post-treatment visits beginning at Day 30 after last treatment received (see Protocol Appendix 7) will be summarized using summary statistics for categorical data for the ES.

Investigator's assessment of product smoothness as measured by the 5-point Likert scale at post-treatment visits beginning at Day 30 after last treatment received (see Protocol Appendix 8) will be summarized using summary statistics for categorical data for the ES.

Investigator assessment of dynamic lip lines upon animation on a 4-point scale at post-treatment visits beginning at Day 30 after last treatment received (see Protocol Appendix 10) will be summarized using summary statistics for categorical data for the ES.

All assessments will be listed for the FAS.

## **9. Safety**

The analysis set used for safety analyses will be the SS. Safety will be assessed on the basis of AE reports and the ISR 30-day diary.

### **9.1. Extent of Exposure**

Subject study product exposure will be summarized using descriptive statistics, separately for each treatment visit and overall for the SS, ES, and PPS. At Visit 1, gauge of cannula used and local anesthetic administered will be summarized using descriptive statistics for categorical data, and total volume administered for this treatment (in mL) will be summarized using descriptive statistics for continuous data. At Visit 2, the number and percentage of subjects receiving touch-up treatment will be presented, and for those subjects, gauge of cannula used and local anesthetic administered will be summarized using descriptive statistics for categorical data, and total volume administered for this treatment (in mL) will be summarized using descriptive statistics for continuous data. At Visit 6, the number and percentage of subjects receiving optional retreatment will be presented, and for those subjects, gauge of cannula used and local anesthetic administered will be summarized using descriptive statistics for categorical data, and total volume administered for this treatment (in mL) will be summarized using descriptive statistics for continuous data. Overall, the total volume administered to each subject (in mL) will be summarized using descriptive statistics for continuous data.

The total volume administered to each subject (in mL) will also be summarized using descriptive statistics for continuous data by presence or absence of an AE for the SS.

Scatter plots of total volume administered to each subject (in mL) vs. FACE-Q score by visit will be presented for the SS with the Pearson correlation coefficient calculated for each visit, separately for each gender and overall.

Treatment administered or reason not completed, date of injection, gauge of cannula used, number of filler syringes used, injection technique(s) used during administration, total volume administered (in mL), and local anesthetic administered will be listed for each subject visit for the SS.

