## **3 STUDY DESIGN**

[figure not shown]
This is a prospective, open-label, multi-centre, interventional, medical device, post-marketing study evaluating the effectiveness of Juvéderm® VOLIFT™ with Lidocaine for lip augmentation. Subjects will attend up to 7 visits: Screening, Initial Treatment, Day 14 (Touch-up, if required), Day 30, Month 3, Month 6, and Month 12. (Study Exit) (see *Figure 3.1*). 60 subjects will be enrolled.

Eligible subjects will undergo treatment with Juvéderm® VOLIFT™ with Lidocaine administered via injection for enhancement as per the current DFU. Fourteen days after the initial treatment, subjects will return to the clinic and the Investigator will assess the effectiveness of treatment. If the Investigator judges that optimum correction has not been achieved, an optional Touch-up treatment may be performed during the Day 14 visit.

Subjects who receive Touch-up treatment at the Day 14 visit will attend their Day 30 visit 30 days after their last treatment (ie, after Touch-up). Similarly, subsequent follow-up visits for those subjects who undergo Touch-up treatment will occur at 3 and 6, and 12 months after the last treatment received.

At 12 months the subject will return to clinic and carry out all assessments. If eligible for treatment as per the VOLIFT Directions For Use and have had no other treatments / medications as described in the Inclusion / Exclusion since 6 months, the subject will be offered a free retreatment injection of Juvéderm® VOLIFT™ with Lidocaine. If the decision is made to not retreat at 12 months, but a later retreatment is planned, then the subject can be treated outside the study with free treatment.

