### 6.2. Key Definitions

A subject is considered 'entered' into the study after the subject has signed the Informed Consent Form (ICF) and a subject number has been assigned.

A subject is considered 'enrolled' after confirmation of participation eligibility and treatment with the investigational product Juvéderm® VOLIFT™ with Lidocaine has occurred during the study.

Study treatment is defined as initial or touch-up treatment with Juvéderm® VOLIFT™ with Lidocaine.

Baseline is defined as the latest assessment prior to any study treatments for each subject.

Study day will be calculated as (date of event or assessment)-(date of first filler treatment)+1 if the event or assessment was on or after the date of the first filler treatment, and as (date of event or assessment)-(date of first filler treatment) if the event or assessment was before the date of the first filler treatment. The day of first filler treatment is Study Day 1 (Visit 1). If a touch-up treatment is administered, Visits 3, 4, and 5 will be 14 days +/- 3 days later than the visit label and window, e.g. the study day for an assessment at Visit 3 (Day 30) could be 44 +/- 10, rather than 30 +/- 7.

End of study is the last clinical visit an enrolled subject has in this study. For subjects who complete this study, the end of study visit will be their Visit 5; for subjects who drop out early, they will be asked to come back for the last clinical visit for end of study data collection.

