#### **7.4. Other Baseline Characteristics**

A urine pregnancy test will be performed by urine dipstick for women of childbearing potential at the screening visit and prior to administration of any study treatment (Day 1 and Day 14, if applicable and at retreatment at Month 12). These data will be listed for women of childbearing potential in the Screened Set.

The POLSS at rest will be assessed at the screening visit and prior to administration of any study treatment at Day 1. The POLSS will be listed for the Screened Set.

No formal statistical testing will be carried out on these data.

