#### 8.2.2. FACE-Q™ – Satisfaction with Lips Questionnaire

Subject's assessment of satisfaction with treatment of their lips as measured by the change from baseline in the FACE-Q™ Satisfaction with Lips questionnaire at all post-treatment visits. The subject will assess satisfaction using the 10 items on the Satisfaction with Lips questionnaire of the FACE-Q™ (see Protocol Appendix 5). The responses to the items will be combined to create a Rasch transformed scale score that ranges from 0 to 100. Change from baseline in FACE-Q™ scale score will be calculated as post-treatment FACE-Q™ scale score – baseline FACE-Q™ scale score.

The overall scale score at baseline and at Visits 3, 4, 5, and 6 as well as the change from baseline scores at all post-treatment visits will be summarized using summary statistics for continuous data for the ES. FACE-Q™ responses, scale scores and changes from baseline will be listed for the FAS.

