### **9.3. Adverse Events**

Throughout the course of the study (from the date of informed consent), all AEs will be monitored and recorded in source documents and on the AE eCRF. All AEs related to study treatments or procedures will be followed until resolved or stabilized based on the Investigator's clinical judgement.

AEs will be coded using MedDRA version 21.0 or higher, and presented by SOC and PT.

AEs will be defined as treatment-emergent if they start after the first treatment. AEs with missing or partial dates will be handled according to Section 6.3 with respect to assigning treatment-emergence. As a conservative approach, AEs are considered treatment-emergent unless there is clear indication that the event occurred before the first treatment in the study. In general, only TEAEs will be included in the summary tables, but all AEs will be included in the listings.

Treatment-related AEs are defined as AEs with a relationship to the study treatment of possible, probably or causal. Procedure-related AEs are defined as AEs with a relationship to the study procedure of

possible, probably or causal. Missing relatedness will not be imputed for the summarization of treatment-related or procedure-related events.

AEs increasing in severity will not be recorded as separate AEs. Missing severity will not be imputed when summarizing events by maximum severity.

At each level of summarization, summaries will include the number of subjects and the number of events. Events increasing in severity will only be counted once. For summaries by SOC and PT, a subject will be counted once at the SOC level and once at each PT within the SOC level. For summaries by SOC, PT, and maximum severity (mild, moderate, severe), a subject will be counted once at the highest severity level for which the event occurred at the SOC level and the highest severity level for each unique PT within that SOC level. Therefore, subjects will only contribute once to each PT and once to each SOC level. Summaries by SOC, PT, and maximum relationship (not related, unlikely, possible, probable, causal relationship) will be handled similarly to the summaries by maximum severity. Summaries presenting frequency of AEs by SOC and PT will be ordered by overall descending frequency of SOC and then, within a SOC, by overall descending frequency of PT.

The following tables will be produced:

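### SAP 9.1 sets no cut-off for total volume, so Month 12 retreatment volume appears to enter FACE-Q correlations and an AE comparison that it follows in time

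*SAP*

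**What the plan says.** - **Exposure, SAP 9.1.** Volume is summarized at Visit 1, at Visit 2 for touch-ups, and at the Month 12 visit: "At Visit 6, the number and percentage of subjects receiving optional retreatment will be presented", with the volume given to those subjects. The next sentence reads: "Overall, the total volume administered to each subject (in mL) will be summarized".
- **Uses of that total, SAP 9.1.** The same per-subject total is compared by presence or absence of an AE (Table 14.3.4.4). It is also plotted against satisfaction: "Scatter plots of total volume administered to each subject (in mL) vs. FACE-Q score by visit will be presented for the SS" (Figure 14.3.4.5), with a Pearson coefficient per visit, by gender and overall. Neither these sentences nor the titles in SAP 15 and 16 limit the volume by visit or date.
- **FACE-Q timing, SAP 8.2.2.** The summary covers "The overall scale score at baseline and at Visits 3, 4, 5, and 6".
- **Month 12 order, Protocol 3.** "At 12 months the subject will return to clinic and carry out all assessments". The offer of retreatment to eligible subjects comes in the sentence after that.
- **Study treatment.** SAP 6.2: "Study treatment is defined as initial or touch-up treatment". SAP 7.4, on pregnancy testing: "prior to administration of any study treatment (Day 1 and Day 14, if applicable and at retreatment at Month 12".
- **AEs.** SAP 9.3: "AEs will be defined as treatment-emergent if they start after the first treatment". Protocol Table 9.1 ends collection of AEs at the last visit, and of serious events 30 days later.
- **Interim, SAP 10.** All indexed tables, figures and listings are also produced at the Month 6 interim from the data then available.

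**The concern.** A coefficient that pairs a satisfaction score with product injected after the score was recorded cannot say how volume relates to satisfaction. Yet that is how readers will take a plot of volume against FACE-Q by visit. Retreatment is optional, and a subject's satisfaction could plausibly influence whether it is accepted. If so, the added volume would carry an association running from score to volume, and would not just be noise.

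The interim makes this visible. A Visit 3 coefficient could change between the interim and final reports under the same figure title, with the same scores and the same volumes given beforehand. In the AE table, a volume difference could arise only because subjects with and without an AE took up retreatment at different rates.

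Only descriptive outputs are at stake. The Protocol Summary says that no formal hypothesis testing is planned, and neither the primary nor the secondary endpoints use volume.

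**Working it through.** **1. Which volumes are in the total.** SAP 9.1 goes through Visits 1, 2 and 6 and then gives an overall total, so the natural reading is V1+V2+V6. The definition in SAP 6.2 would exclude Visit 6, but the sentences on total volume do not use the term it defines. SAP 7.4 uses that term to include Month 12. The visible text therefore supports inclusion without settling it.

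**2. What comes first.**

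| Outcome | Relation to Visit 6 volume | Basis |
|---|---|---|
| FACE-Q, Visits 3 to 5 | before | visit schedule |
| FACE-Q, Visit 6 | before | sentence order in Protocol 3 only |
| Non-serious AEs | nearly all before | collection ends at last visit |
| Serious AEs | mostly before | 30 further days only |

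**3. Interim against final.** V1 and V2 volumes and Visit 3 to 5 scores are complete by the interim. Visit 6 volume is still accruing. Any change in the Visit 3 to 5 coefficients between reports that is due to Visit 6 volume is purely an effect of the definition. Sampling error cannot explain it, because the subjects and scores are the same.

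**4. Possible size for FACE-Q.** The plan gives no figure here to reproduce. It gives no volume SD, retreatment uptake, mean retreatment volume, or link between score and uptake. All inputs below except n=60 are assumptions.

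- V1+V2 volume has SD 0.5 mL and true correlation r with the plotted score (0 or 0.30).
- Retreatment has mean m = 0.5 or 1.0 mL, SD 0.3m and uptake p = 20%, 50% or 80%.
- Uptake is logistic in the Month 12 score z, with slope 0, ±0.35 or ±0.7 per SD.
- The plotted score correlates ρ with z: 1 for Visit 6, and 0.7, 0.5 or 0.3 for Visits 3 to 5.

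Let C be the covariance of z with the uptake indicator, and Var(R) = p(0.3m)² + p(1−p)m². Then

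r_obs = (0.5r + ρmC) / √(0.25 + Var(R) + 2·0.5·r·ρmC).

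*Uptake unrelated to score (C = 0).* A true 0 stays 0. For r = 0.30, with p = 0.2 and m = 0.5: 0.15/√(0.25 + 0.0045 + 0.04) = 0.276. With p = 0.5 and m = 1.0: 0.15/√(0.25 + 0.045 + 0.25) = 0.203. These are the extremes of the grid.

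*Uptake related to score.* The most extreme cell is Visit 6, p = 0.5, m = 1.0, slope −0.7. There C = −0.1575 by numerical integration, and r_obs = (0.15 − 0.1575)/√(0.545 − 0.0473) = −0.01. With slope +0.7 and r = 0: 0.1575/√0.545 = 0.21.

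| Panel | True 0 becomes (absolute) | True 0.30 becomes |
|---|---|---|
| Visit 6 | 0.05 to 0.21 | −0.01 to 0.40 |
| Visits 3 to 5 | 0.015 to 0.15 | 0.06 to 0.35 |

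Fisher-z 95% limits at n=60 (half-width 1.96/√57 on the z scale) are ±0.25 around 0 and 0.05 to 0.51 around 0.30. No true-0 cell lies outside. For true 0.30, 1 of 24 Visit 6 cells and 0 of 72 Visit 3 to 5 cells do.

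A second set of assumptions (V1+V2 SD 0.4 to 0.8 mL, m 0.5 to 1.5 mL with SD 0.4m, uptake 30% to 100%) multiplies r by 0.42 to 0.97 when uptake is unrelated to the score. With SD 0.6 mL, m = 1.0 mL, uptake 50% and slopes up to ±1, a true 0.30 becomes −0.03 to 0.44.

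**5. Possible size for the AE table.** The spurious difference is the uptake difference times the mean retreatment volume. Equal uptake gives 0. Ten points at 0.5 mL give 0.10 × 0.5 = 0.05 mL; thirty points at 1.0 mL give 0.30 × 1.0 = 0.30 mL. These inputs are also assumed.

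**The case against.** The strongest reply is that the answer may lie in text we cannot see. The table shells, figure shell, flowchart and Month 12 visit description are all blanked, and a V1+V2 footnote would sit in just those places. That stands, and it makes the point conditional. A reader might infer that the plan certainly pairs scores with later volume; the visible text does not prove it.

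Second, SAP 6.2 limits study treatment to initial and touch-up injections, and the SAP 7.4 wording is a pregnancy-test schedule, not a definition of exposure. Both statements are fair. But SAP 9.1 does not use the defined term for its total, and it lists Visit 6 volume immediately before that total.

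Third, the SAP never says that the plot is meant to show an effect of volume, and almost every illustrative shift lies inside sampling limits. At Visit 6 fewer than 60 subjects may contribute, because Protocol 6.2.9 makes follow-up past Month 6 subject to a further consent. At an assumed n=40 the limits around 0.30 are −0.01 to 0.56, and no cell of the first grid falls outside. This supports calling the impact low. It does not justify leaving the plotted variable undefined, and it does not touch the interim-to-final discrepancy.

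Finally, a reader might go further on the AE table. AEs count from the first treatment, so one with onset before Day 14 also precedes any touch-up volume, which might suggest splitting the table by onset period with separate comparators. The documents do not call for that. The table is a crude cumulative description, and with 60 subjects the split cells would be sparse. A separate summary of AEs after retreatment would also hold little, since non-serious AE collection stops at the last visit.

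**Conclusion.** The point holds on the visible text and is conditional on the shells. SAP 9.1 leaves total volume without a cut-off. On its natural reading, Figure 14.3.4.5 and Table 14.3.4.4 include retreatment volume given after the Visit 3 to 5 scores and after nearly all AE collection. That it also follows the Visit 6 score rests on sentence order in Protocol 3.

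The impact is low. The outputs are descriptive, the endpoints and sample size are untouched, and V1+V2 volume can be recovered from the per-visit treatment listing (16.2.5). The true size is unknown: the ranges above depend on assumed volumes, uptake and score dependence. A reader might infer that the satisfaction results themselves are biased. They are not: the FACE-Q summaries in SAP 8.2.2 do not involve volume.

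**What to change.** Check the table and figure shells first. Unless they already set a cut-off:

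1. In SAP 9.1, and in footnotes to Figure 14.3.4.5 and Table 14.3.4.4, define the volume used as initial plus touch-up (V1+V2), at both the interim and the final analysis.
2. Report Visit 6 retreatment volume separately, as SAP 9.1 already plans for that visit.
3. Reconcile the uses of study treatment in SAP 6.2 and 7.4, so that it is clear whether the Month 12 retreatment is covered.

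The AE table keeps its single comparison. The cost is one definition, two footnotes and minor programming, with no new data.

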### **3.6. Treatment Assignment & Blinding**

This is an open-label, single-arm study. Thus, blinding and randomization methods will not be implemented.

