### **3.7. Administration of Study Medication**

[figure not shown]
The Investigator will determine the appropriate volume of Juvéderm® VOLIFT™ with Lidocaine to be injected to augment the lips (e.g., add fullness). It is anticipated that the volume of Juvéderm® VOLIFT™ with Lidocaine to be injected for lip augmentation will not exceed 3.0mL total per subject.

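### The volume versus FACE-Q correlations ignore baseline FACE-Q and the timing of volume, so the raw r can understate the association at equal baseline

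*SAP*

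**What the plan says.** SAP Section 9.1 (Extent of Exposure) plans "Scatter plots of total volume administered to each subject (in mL) vs. FACE-Q score by visit" for the Safety Analysis Set, "with the Pearson correlation coefficient calculated for each visit, separately for each gender and overall". The variable named is the score, not its change from baseline, and no covariate or stratification is specified.

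On how volume arises:

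- SAP Section 3.6: "This is an open-label, single-arm study".
- SAP Section 3.7: "The Investigator will determine the appropriate volume of Juvéderm® VOLIFT™ with Lidocaine", with an anticipated amount that "will not exceed 3.0mL total per subject".
- Protocol Section 3: "If the Investigator judges that optimum correction has not been achieved, an optional Touch-up treatment may be performed during the Day 14 visit".

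Baseline FACE-Q is available. SAP Section 8.2.2 summarises it and defines change from baseline for Visits 3 to 6. SAP Section 8 has efficacy analyses refer back to each subject's own baseline, but this figure sits in Section 9 (Safety), so that rule does not clearly reach it. The baseline LFS2 subgroups in SAP Section 6.6 apply to tables, not figures.

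**The concern.** A correlation between volume and later satisfaction invites the reading that more product does, or does not, go with a happier subject. Volume here reflects a judgement about each subject. If that judgement gives more product to subjects who start with lower satisfaction, and low starters tend to stay lower, the raw r combines two things: how volume was allocated, and how volume relates to satisfaction among comparable subjects. The first pulls r down and can mask the second.

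There is also a timing question. SAP Section 9.1 uses total volume per subject for the overall exposure total, straight after describing the optional Visit 6 retreatment. On its plain reading, the plot could set scores against product injected after those scores were recorded.

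At stake is how one exploratory figure is interpreted. A raw r near zero could be reported as no relation between volume and satisfaction when the relation at equal baseline is positive.

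**Working it through.** **The plan's own figure.** None is given for this correlation. The only stated precision figure is the 10% margin for an 80% responder rate with 60 subjects (SAP Section 3.5). It reproduces: 1.96 × √(0.8 × 0.2 / 60) = 0.101. It does not bear on the correlation.

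**Inputs.** From the documents: 60 subjects, FACE-Q level against total volume, no adjustment. Assumed, because the documents give no values: rho, the correlation of baseline FACE-Q with volume; b, the weight of baseline on the later score; g, the volume effect at equal baseline. All variables are standardised, with equal SDs for baseline and later score.

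**Formulas.** Later score = g × volume + b × baseline + error. Then:

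- raw r = g + b × rho
- correlation of later score with baseline, c = b + g × rho
- partial r = (raw r − rho × c) / √[(1 − rho²)(1 − c²)]
- r of volume with change = (raw r − rho) / √(2 − 2c)

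**Worked example, rho = -0.4, b = 0.5, g = 0.2.**

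- raw r = 0.2 + 0.5 × (-0.4) = 0.00
- c = 0.5 + 0.2 × (-0.4) = 0.42
- partial r = (0 + 0.4 × 0.42) / √(0.84 × 0.8236) = 0.168 / 0.832 = 0.20
- change r = 0.4 / √1.16 = 0.37

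**Same rho and b, no volume effect (g = 0).** Raw r = -0.20, change r = 0.20 / √1 = +0.20, partial r = 0. Correlating volume with change therefore does not solve the problem; it errs in the other direction.

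**Range.** For g = 0.1, 0.2, 0.3; b = 0.2, 0.4, 0.6; rho = 0, -0.1, -0.2, -0.3, -0.5 (45 combinations), raw r runs from -0.20 to 0.30 and partial r from 0.09 to 0.38. Raw r is exactly zero at 3 combinations and negative at 6. A negative sign needs b × |rho| > g. At rho = 0 and g = 0.2, raw r is 0.20 and partial r 0.20 to 0.25, so there is no material distortion.

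**Sampling error at n = 60.** The 95% half-width for r near 0 is tanh(1.96 / √57) = 0.25; an r of 0.20 has an interval of about -0.06 to 0.43. In 20,000 simulated studies of 60 subjects, r was zero or negative this often:

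| g, b, rho | raw r ≤ 0 | partial r ≤ 0 |
|---|---|---|
| 0.2, 0.4, -0.3 | 27% | 6% |
| 0.2, 0.6, -0.5 | 78% | 6% |

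**Timing, passages side by side.** SAP Section 6.2 limits study treatment to the initial and touch-up injections. SAP Section 9.1 lists Visit 6 retreatment volume and then summarises an overall total per subject. Protocol Section 3 places the 12-month assessments before the retreatment offer. If the plotted total includes retreatment, scores at Visits 3 to 6 are all correlated with later product. SAP Section 10 also has every figure produced at the 6-month interim, so the Visit 3 coefficient could change between interim and final with no change in Visit 3 FACE-Q data.

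**The case against.** The strongest reply is that the premise is not in the documents. The investigator judges lips; FACE-Q is the subject's own satisfaction score. Nothing in either document says volume follows baseline FACE-Q, and rho could be near zero. This stands, and it makes the point conditional. The figure shells are not visible, so a baseline panel that would show rho cannot be ruled out. Such a panel would still leave the later coefficients unadjusted.

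A second reply is that the raw r is a valid description of the crude association, which is all a descriptive study promises. The Protocol Summary rules out formal testing, the correlation is not an endpoint, and the interval of about ±0.25 is wider than the 0.20 gap in the example. Volumes and FACE-Q scores are listed by subject, so an adjusted analysis could be run later. All of this stands and limits the importance. It does not argue against printing the adjusted figure beside the crude one.

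A third reply concerns the remedy. Touch-up volume is added when early correction is judged insufficient, so a poor early response raises total volume. That selection arises after baseline, and adjusting for baseline FACE-Q leaves it in place. This also stands and governs how the adjusted r must be labelled.

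**Conclusion.** The point holds as a minor, conditional one. The planned coefficient omits a baseline measure that is already collected, for an exposure that was not assigned. If rho is negative and baseline carries forward, the raw r is pulled below the association at equal baseline by b × |rho|, which is 0.20 in the worked example. The values of rho, b and g are all assumptions. The timing ambiguity does not depend on them.

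Three stronger readings do not follow:

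- A reader might infer that the planned r will show the wrong sign. That requires b × |rho| > g. The worked example shows masking, and only 6 of the 45 assumed combinations show reversal.
- A reader might infer that baseline adjustment gives the effect of volume. It does not, because of touch-up selection.
- A reader might infer that this is the plan's only use of volume as an explanatory variable. SAP Section 9.1 also summarises volume by presence or absence of an adverse event; the FACE-Q plot is the only analysis of volume against efficacy.

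The primary endpoint and its analysis are unaffected.

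**What to change.** Keep the scatter plots and raw r in SAP Section 9.1 and add:

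- for each post-treatment visit, the partial correlation of FACE-Q score with volume, adjusted for baseline FACE-Q, with a 95% CI;
- a definition of the plotted volume as product given before that visit's assessment, which excludes Visit 6 retreatment;
- a footnote that both coefficients are descriptive and not causal, because touch-up volume depends on early response and baseline adjustment does not remove that selection.

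The cost is a sentence or two in the SAP, a PARTIAL statement in the SAS correlation step and a footnote, using data already collected. The downside is slightly more output and some risk that the adjusted r is over-read, which the interval and the footnote are meant to limit.
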